### **5.2.6. Weekly Percentage of Heavy Drinking Days and Weekly Percentage of Days Abstinent**

Weekly percentage of heavy drinking days is the number of heavy drinking days in a 7-day period divided by 7 then multiplied by 100. The TLFB permits capturing data in a subsequent visit if a visit is missed; however, if fewer than 7 days are observed then the denominator is the number of days observed in the 7-day period. At least 3 days in a week must be observed; otherwise, the week is considered missing.

Weekly percentage of days abstinent is similarly calculated by using the number of days abstinent instead of the number of heavy drinking days.

### **5.2.7. Weekly Mean Number of Drinks and Weekly Mean Number of Drinks per Drinking Day**

Weekly mean number of drinks is the sum of SDUs calculated to the tenths over 7 calendar days divided by the number of days with non-missing data. The quotient is multiplied by 7. At least 3 days in a week must be observed; otherwise, the week is considered missing.

Weekly mean number of drinks per drinking days utilizes the same numerator, and the denominator is the number of days with greater than 0 SDUs. Weeks where all days within the week are abstinent are assigned a value of 0 for weekly drinks per drinking day.

### **5.2.8. World Health Organization Drinking Risk Categorical Scale**

The WHO has developed a drinking risk categorical scale that can be used in a responder analysis approach to assess clinically relevant decreases in alcohol consumption ([Aubin et al-2015](#)). Two dichotomous endpoints will be analyzed: WHO 1-level and WHO 2-level decrease in alcohol consumption. The WHO 1-level and 2-level decrease endpoints are the percentage of subjects experiencing at least a 1-level or 2-level decrease in WHO levels of alcohol consumption, respectively, from the level at baseline (the period including the 28 days before screening) to the level during the last 4 weeks of the maintenance phase (Study Weeks 2-5). The WHO levels of average alcohol consumption per day are as follows:

	Males	Females
Low Risk	1 to 40g	1 to 20g
Medium Risk	41 to 60g	21 to 40g
High Risk	61 to 100g	41 to 60g
Very High Risk	101+g	61+g

where 14g = 1 SDU ([WHO-2000](#)). In computing the alcohol consumption level, average drinks per day will be used, computed as the sum of all drinking in the 28 day period divided by the number of days with non-missing drinking data in that period. Abstinent subjects will be included in a separate “Abstinent” category. A subject must have at least 1 week of data during the last 4 weeks of the maintenance phase to be considered non-missing.

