
Number of Subjects (Planned): 60
Main Inclusion/Exclusion Criteria: Subjects will be male and female at least 21 years of age with 4 or more DSM-5™ symptoms of AUD (moderate to severe AUD). They must also be seeking treatment for AUD and if male, report drinking an average of at least 28 drinks per week or if female report drinking an average of at least 21 drinks per week prior to consent, and have at least 1 heavy drinking day (4 or more drinks per day for women/5 or more drinks per day for men) during the 7-day period prior to randomization.
Investigational Product, Dosage and Mode of Administration: The target doses are 25 mg tablet of ASP8062 by oral administration once daily at bedtime for 6 weeks.
Reference Therapy, Dosage and Mode of Administration: Subjects in the placebo group will take an equivalent number of identically matched placebo tablets (one per day) by oral administration once daily at bedtime for 6 weeks.
Duration of Study: Each subject will participate in the study for up to 11 weeks, including up to 2 weeks of screening, 6 weeks of treatment, one end-of-study visit during the week following the last treatment dose, and a final telephone contact ~2 weeks after completing treatment for a safety follow-up.

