### **9.4.3. Analysis of the Secondary Efficacy Endpoints**

Secondary efficacy endpoints will also be analyzed based on data collected during the last 4 weeks of the maintenance period (Weeks 3 through 6), including TLFB and other questionnaire data assessed at Week 7 that reflect data collected during this period. Note that the data collected at Week 7 reflect drinking and other questionnaire items that occurred during Week 6.

In general, every continuous secondary efficacy endpoint is analyzed using a repeated measures mixed effects model where subjects are random effects; factors and covariates are fixed effects. The analyses will be performed using SAS PROC MIXED procedure. The information criterion is requested from every mixed effects model. Subjects are treated as a class variable and not continuous. The week (Weeks 3 through 6), treatment group, and clinical site are also treated as class variables.

The primary analysis model for all continuous endpoints is:

- Appropriately transformed endpoint = treatment + week + treatment\*week + clinical site + baseline equivalent of endpoint + other covariates (identified in Section 9.4.4)

This model will also be created for the untransformed endpoint. The solution statement from SAS PROC MIXED is requested to provide the solution for the fixed effects parameters. A

REPEATED statement specifies that values are repeated each week and subjects are nested within treatment group. The covariance structure is specified.

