#### **9.4.3.1. Secondary Drinking Endpoints**

Percentage of days abstinent per week, percentage of subjects abstinent, percentage of heavy drinking days per week, percentage of very heavy drinking days, weekly mean number of drinks per week, and weekly mean number of drinks per drinking day will be analyzed using the mixed effects model specified in Section 9.4.3. Covariates for these models will be identified as in Section 9.4.4.

Percentage of subjects with a WHO 1-level decrease, and WHO 2-level decrease in alcohol consumption risk category will be analyzed during the last 4 weeks of the maintenance period (Weeks 2 through 5) using a logistic regression model. Covariates for the logistic regression will be identified as in Section 9.4.4. 2x2 contingency tables will report the WHO 1-level decrease, and WHO 2-level decrease along with Cohen's h, odds ratios and 95% CIs. The Wald statistic will be used to test for treatment differences.

No adjustment for multiple comparisons and no imputation will be used for these endpoints.

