**Table 70: WHO 1-Level Decrease in Alcohol Consumption (mITT) – Weeks 3-6**

	ASP8062	Placebo	Total
	(N=xx)	(N=xx)	(N=xxx)
WHO 1-Level Decrease			
Yes	xx (xx.x%)	xx (xx.x%)	xx (xx.x%)
No	xx (xx.x%)	xx (xx.x%)	xx (xx.x%)

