**Table 71: WHO 1-Level Decrease in Alcohol Consumption (mITT) – Full Model, Logistic Regression, Weeks 2-5**

									95% CI 	
Parameter		DF 	Estimate	Standard Error	Wald Chi-Square	Pr > Chi-Square	Cohen's h	OR 	Upper	Lower
Intercept		1	xx.XXX	xx.XXX	xx.XXX	0.xxx				
Treatment	Overall	X	xx.XXX	xx.XXX	xx.XXX	0.xxx				
Treatment 	ASP8062	X	xx.XXX	xx.XXX	xx.XXX	0.xxx	0.xxx	xx.XXX	xx.XXX	xx.XXX
Site	Overall	X	xx.XXX	xx.XXX	xx.XXX	0.xxx				
Site 	1	X	xx.XXX	xx.XXX	xx.XXX	0.xxx		xx.XXX	xx.XXX	xx.XXX
Site	2	X	xx.XXX	xx.XXX	xx.XXX	0.xxx		xx.XXX	xx.XXX	xx.XXX
Cov		X	xx.XXX	xx.XXX	xx.XXX	0.xxx		xx.XXX	xx.XXX	xx.XXX

 DF is degrees of freedom;  OR is odds ratio;  CI is confidence interval;  Comparison to placebo;

 Site 3 is reference for the OR

*Programming note: COV is baseline equivalent of dependent variable and any other covariate(s) which have not been specified at the time of writing of SAP*

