**Table 72: WHO 2-Level Decrease in Alcohol Consumption (mITT) – Weeks 3-6**

Same as Table 70

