**Table 73: WHO 2-Level Decrease in Alcohol Consumption (mITT) – Full Model, Logistic Regression, Weeks 3-6**

Same as Table 71

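### The SAP sets the WHO responder window as Weeks 2-5 in three places, but the last 4 of 6 treatment weeks are Weeks 3-6

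*SAP*

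**What the plan says.** Two windows are given for the same two endpoints.

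**Weeks 2-5**
- SAP 5.2.8, the endpoint definition: "last 4 weeks of the maintenance phase (Study Weeks 2-5").
- SAP 9.4.3.1, the analysis section, for both WHO endpoints: "during the last 4 weeks of the maintenance period (Weeks 2 through 5) using a logistic regression model".
- Table 71, the 1-level model, in the shell and in the List of Tables: "WHO 1-Level Decrease in Alcohol Consumption (mITT) – Full Model, Logistic Regression, Weeks 2-5".

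**Weeks 3-6**
- SAP 9.4.3, the general rule for secondary endpoints: "data collected during the last 4 weeks of the maintenance period (Weeks 3 through 6").
- Table 70, the 1-level counts: "WHO 1-Level Decrease in Alcohol Consumption (mITT) – Weeks 3-6".
- Table 72, the 2-level counts: "WHO 2-Level Decrease in Alcohol Consumption (mITT) – Weeks 3-6".
- Table 73, the 2-level model: "WHO 2-Level Decrease in Alcohol Consumption (mITT) – Full Model, Logistic Regression, Weeks 3-6". Its shell, however, only refers the programmer back to Table 71.

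The protocol synopsis has the tablets taken "by oral administration once daily at bedtime for 6 weeks", and the SAP exposure shell (Table 2) gives a maximum of 42 tablets. The protocol analyses the secondary endpoints, with the WHO shifts named among the dichotomous ones, over the last 4 weeks of the treatment period. SAP 3.3.2 agrees.

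**The concern.** Weeks 2-5 are the last 4 weeks of a 5-week treatment period, not of a 6-week one. The documents define no separate maintenance phase that ends at Week 5, and SAP 9.4.3 attaches the same maintenance wording to Weeks 3-6. A deliberate WHO-specific window is unlikely, because three of the four WHO table titles say Weeks 3-6.

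Three things are at stake.

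- **The wrong 28 days.** Timeline follow-back data exist for both windows, so code written from the endpoint definition would run normally on Weeks 2-5.
- **Counts and model that need not match.** With titles taken literally, the 1-level odds ratio in Table 71 rests on different days from the counts in Table 70. For the 2-level endpoint, both titles conflict with the text in 5.2.8 and 9.4.3.1.
- **A choice left open.** If the conflict is settled after unblinding, it becomes a choice between two written windows made with results in view.

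Both endpoints compare a 28-day average with fixed cut-points, so a different 28 days can move a subject across a category boundary. The window can also change who counts as non-missing, because 5.2.8 requires at least one week of data within it.

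**Working it through.** **1. Which weeks are the last four.** For T weeks of treatment, the last 4 weeks are Weeks T-3 to T. The SAP's figure of Weeks 2-5 is reproduced only with T = 5 (35 daily tablets). The documents give T = 6 (6 x 7 = 42 tablets), so the answer is Weeks 3-6.

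**2. Overlap in days.** In the Schedule of Assessments, week w covers Days 7(w-1)+1 to 7w.

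| Window | Days | Length |
|---|---|---|
| Weeks 2-5 | 8-35 | 28 |
| Weeks 3-6 | 15-42 | 28 |
| Shared | 15-35 | 21 |

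Days 8-14 are wrongly included and Days 36-42 are left out: 7/28 = 25%.

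**3. Shift in the daily average.** With complete data and 14 g per drink (SAP 5.2.8), the two averages differ by

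(Week 2 drinks - Week 6 drinks) x 14 g / 28 days = (Week 2 - Week 6)/2 g/day.

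| Week 2 minus Week 6 (drinks) | Shift (g/day) | Share of a 20 g band | Share of the men's 40 g High Risk band |
|---|---|---|---|
| 4 | 2 | 10% | 5% |
| 10 | 5 | 25% | 12.5% |
| 14 | 7 | 35% | 17.5% |

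**4. One subject (assumed values).** A man in the Very High category at baseline averages 112, 98, 98, 98 and 70 g/day in Weeks 2 to 6.
- Weeks 2-5: (112 + 98 + 98 + 98)/4 = 101.5 g/day. Very High, so not a responder.
- Weeks 3-6: (98 + 98 + 98 + 70)/4 = 91.0 g/day. High, so a 1-level responder.

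**5. How many subjects could switch (all inputs assumed).** I simulated 400,000 subjects in each of 18 scenarios:
- 60% men; baseline drinks per week = 28 (men) or 21 (women) x exp(|N(0, 0.5)|);
- on-treatment fraction of baseline N(1 - reduction, 0.3), truncated at 0, with a reduction of 30% or 50%;
- lognormal weekly variation with CV 20%, 35% or 50%, independent between weeks;
- linear decline from Week 2 to Week 6 of 0%, 20% or 40%, with the Weeks 2-6 mean held fixed.

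Responder status differed between the windows in 3.3-12.7% of subjects (1-level) and 2.8-9.2% (2-level). Out of 60, that is about 2 to 8.

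| Decline, Week 2 to Week 6 | Responder rate, Weeks 3-6 minus Weeks 2-5 |
|---|---|
| 0% | about 0 points |
| 20% | 2.8 to 5.0 points |
| 40% | 6.3 to 11.0 points |

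No difference between arms was simulated.

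**6. Missing data.** Take a subject whose data end at the Week 3 visit, on Day v (15 to 21). Completed days number v - 8 in Weeks 2-5 (7 to 13) and v - 15 in Weeks 3-6 (0 to 6). If one week of data means 7 days, this subject is non-missing under Weeks 2-5 and missing under Weeks 3-6. If it follows the 3-day rule of SAP 5.2.6 and 5.2.7, only visits on Days 15, 16 or 17 give a missing value under Weeks 3-6. A final visit after early discontinuation, or later follow-back capture, would add days.

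**The case against.** The mismatch itself is hard to dispute. The case against giving it weight is as follows.

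- **The intent is recoverable.** Both defective sentences say last 4 weeks, the SAP expands on the protocol, and 9.4.3.1 sits under 9.4.3, which gives Weeks 3-6. Only the numerals are wrong. This is fair, and it shows which way to correct. But the definition and the analysis section are what a programmer works from, and they agree with each other.
- **The error is visible.** Tables 70 and 71 are adjacent and carry different week ranges, and SAP section 10 requires tables to be reviewed for consistency with the plan. This stands in part. Detection is not assured when the plan to be checked against says both things.
- **The percentages rest on assumptions.** This stands. If weekly deviations are correlated at 0.8 instead of independent, the low end of switching falls to about 1.3%. The figure of 60 is an upper limit, because the analysis uses mITT subjects with enough drinking data. The shift formula needs complete data.
- **No inferential harm is shown.** This stands. Two of 15 secondary endpoints are affected, with no multiplicity adjustment, and no between-arm effect has been demonstrated.
- **The missing-data case is narrow.** This also stands. The number of such subjects is unknown, and one week of data needs defining under either window.

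**Conclusion.** The inconsistency is real and should be fixed. It rests on the text and calendar arithmetic alone: with 6 weeks of treatment, Weeks 2-5 are not the last 4 weeks, and following SAP 5.2.8 and 9.4.3.1 literally would score two secondary endpoints on a window that differs from the protocol's in a quarter of its days.

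The effect on results is less certain. If drinking falls between Week 2 and Week 6, Weeks 2-5 gives a lower responder rate than the protocol's window. If it does not, switches in the two directions cancel. The simulated sizes are illustrations under stated assumptions, not predictions. The primary endpoint, its power and its type I error do not depend on this window.

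**What to change.** Before unblinding:

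1. Replace Weeks 2-5 with Weeks 3-6 (Days 15-42) in SAP 5.2.8, SAP 9.4.3.1, the Table 71 title and its entry in the List of Tables.
2. Confirm that Table 73, whose shell refers to Table 71, is run on Weeks 3-6 as its title says.
3. State in SAP 5.2.8 how many observed days make one week of data.

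The cost is SAP wording, one table title and programming notes. Data collection and sample size do not change.

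Three related labels should be corrected at the same time, although they carry no weight in this point. SAP 3.3.1 and the visit label in Listing 16 place the treatment cue session at Week 2, whereas the protocol, the schedule, SAP section 7 and Table 34 place it at Week 3. The Figure 3 note stops at 5 weeks and should run to 6.

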### **5.3. Alcohol-Related Craving, Consequences, and Withdrawal**

Alcohol-related craving is measured using the ACQ-SF-R scale and PACS; alcohol-related consequences are measured using the PROMIS Alcohol Negative Consequences scale; and alcohol-related withdrawal is measured using the CIWA-AR scale. The PACS and PROMIS

Alcohol Negative Consequences are used as efficacy endpoints, while the ACQ-SF-R and CIWA-AR scales are safety endpoints.

The ACQ-SF-R contains 12-items adapted from the 47-item ACQ-NOW developed by [Singleton et al \(1994\)](#) to assess craving for alcohol among alcohol users in the current context (right now). Items 3, 8, and 11 are reverse keyed. A general craving index is derived by summing all items and dividing by 12. If an item is missing, then the number of items is reduced by the number missing, and the sum is only the sum of the answered items. At least 10 items must be endorsed for the general craving index of ACQ-SF-R to be considered non-missing (i.e., scored).

The PACS is a five-item self-administered instrument for assessing craving ([Flannery-1999](#)). Frequency, intensity, and duration of thoughts about drinking are assessed along with ability to resist drinking. The final item asks the responder to provide an average rating of his/her craving over the course of the past week. The questions on the PACS use descriptors coupled with numerical ratings ranging from 0 to 6. The items are summed for a total score.

PROMIS Alcohol Negative Consequences scale is for negative consequences from alcohol use. The short form of the PROMIS Alcohol Negative Consequences questionnaire will be used to assess outcomes of alcohol use over the past 30 days ([Pilkonis-2013](#)).

The 7 PROMIS items include:

- Drinking created problems between me and others
- I disappointed others when I drank
- I was unreliable after I drank
- Others complained about my drinking
- I used poor judgment when I drank
- I said or did embarrassing things when I drank
- I had trouble getting things done after I drank

Each item is rated on a 5 point scale including: Never (1), Rarely (2), Sometimes (3), Often (4), and Almost Always (5) for the past 30 days. A subject's total score is converted to a T-score using scoring table provided by NIH PROMIS.

The CIWA-AR modified telephone version is an adaptation for telephone administration of the CIWA-AR a brief 10-item measure used to provide a quantitative index of the severity of the alcohol withdrawal syndrome ([Sullivan et al-1989](#)). The CIWA-AR has been used both in clinical and research applications and has demonstrated both reliability and validity ([Sellers et al-1992](#), [Stuppaec et al-1994](#)). The total score is the sum of the individual item scores. Since this is an interview scale, no missing items are anticipated. A score  $\geq 10$  is considered an indication that the subject is undergoing alcohol withdrawal.

#### 5.4. Mood

Mood will be measured with the POMS, while negative emotional state will be measured using an exploratory measure of hyperkatifeia.

The POMS measures dimensions of affect or mood ([McNair and Heuchert-2005](#)). It consists of 65 adjectives to which the subject responds according to a 5-point scale ranging from “not at all (0)” to “extremely (5).” Six subscale scores will be computed for items grouped as follows: Tension-Anxiety, Depression-Dejection, Anger-Hostility, Vigor-Activity, Fatigue-Inertia, and Confusion-Bewilderment. A Total Mood Disturbance score will also be computed which consists of the sum of Tension-Anxiety, Depression-Dejection, Anger-Hostility, Fatigue-Inertia, and Confusion-Bewilderment scores then subtracting the Vigor-Activity subscale score. A missing value within a subscale will be replaced by the average score of the answered items within the subscale; if 2 or more items within a subscale are missing then the entire subscale is missing ([Macefield et al-2010](#)).

Hyperkatifeia is defined as a greater intensity of negative emotional/motivational signs and symptoms during withdrawal from drugs of abuse in the withdrawal/negative affect stage of the addiction cycle ([Koob-2021](#)). Hyperkatifeia or negative emotional state is considered to be one of stages of addiction in the context of drug withdrawal ([Koob and LeMoal-1997](#), [Koob-2019](#)). NIAAA has developed a 24-item self-report Hyperkatifeia Scale to capture negative emotionality after stopping alcohol drinking that will be assessed for the first time in this study of heavy drinkers with a diagnosis of moderate to severe AUD. The items address four measures associated with negative emotional state including stress/anxiety, depression, stress, irritable and pain.

One difference between this scale and other negative emotional state scales is the pain questions. Pain may be particularly important in AUD as there is a positive association between pain severity and a higher risk for AUD ([Lawton and Simpson-2009](#), [Edlund et al-2013](#)). Also, physical pain appears to be a significant predictor of alcohol use and heavy alcohol use and relapse to drinking after a period of abstinence ([Larson et al-2007](#), [Caldeiro et al-2008](#), [Witkiewitz et al-2015](#)).

## **5.5. Sleep Quality**

Sleep quality will be measured using the PSQI. The PSQI is a 19-item questionnaire ([Buysse et al-1989](#)). The addition of all the scores permits an analysis of the subject’s overall sleep experience in the past 30 days. The lower the overall score, the better the person sleeps. A score  $\geq 5$  is indicative of a sleep disturbance. If any of the items is missing, then the entire form is missing for that evaluation (PSQI website).

## **5.6. Cigarette Smoking Quantity-Frequency and Nicotine Use Questionnaire**

A smoking quantity frequency and nicotine use interview will include 3 questions to assess nicotine use via cigarette smoking or via other products during the study: 1) Over the past week, on how many days did you smoke cigarettes?; 2) On the days you smoked during the past week, how many cigarettes did you smoke on average?; and 3) Over the past week, on how many days did you use other nicotine products (ex. chew, cigars, cigarellos, e-cigarettes, vape, gum, patch, etc...)? At baseline subjects that answer “0” to question #1 are considered non-smokers for the study. Cigarettes per week is the answer to question #1 multiplied by the answer to question #2. At baseline, subjects who report smoking (question #1) or the use of other nicotine product (question #3) will be considered nicotine users. The responses to questions #1 and #3 will be

used to calculate the percentage of subjects abstinent from nicotine use among nicotine users. No imputation for missing values will be used.

## 6. HYPOTHESES TO BE TESTED

### 6.1. Primary Efficacy Endpoint

Subjects treated with ASP8062 will report significantly lower VAS alcohol craving ratings in response to the *in vivo* alcohol cue during the treatment human laboratory cue session than placebo-treated subjects.

The hypotheses for the confirmatory secondary endpoints for the cue reactivity sessions are the same as for the primary endpoint.

### 6.2. Secondary Efficacy Endpoints

It is hypothesized that, during the last 4 weeks of the treatment period, ASP8062 as compared to the placebo, will:

1. Increase the percentage of subjects with no heavy drinking days. A “heavy drinking day” is 4 or more drinks per drinking day for women and 5 or more drinks per drinking day for men.
2. Increase the percentage of subjects abstinent from alcohol
3. Increase the percentage of subjects with at least a WHO 2-level decrease in alcohol consumption
4. Increase the percentage of subjects with at least a WHO 1-level decrease in alcohol consumption
5. Increase the percentage of days abstinent per week
6. Decrease the percentage of heavy drinking days per week
7. Decrease the percentage of very heavy drinking days per week
8. Decrease the weekly mean number of drinks per week
9. Decrease the weekly mean drinks per drinking day
10. Decrease the weekly mean cigarettes smoked per week among smokers
11. Increase the percentage of subjects abstinent from nicotine use among subjects who used any nicotine products in the week before randomization
12. Decrease the mean alcohol craving score (PACS)
13. Decrease the mean PSQI score
14. Decrease total mood disturbance (POMS)
15. Decrease in alcohol negative consequences (PROMIS)

